9.2 Secondary Efficacy Analyses

Analyses relating to secondary efficacy variables, the cumulative proportions of subjects achieving hemostasis by other individual assessment times (i.e., 7 minutes and 10 minutes), will be similarly analyzed using CMH test.

The proportion of subjects with treatment failures will be summarized and analyzed using CMH test.

9.3 Exploratory Efficacy Analyses

Exploratory efficacy endpoints will be descriptively summarized by treatment group. The proportion of subjects achieving at least 1 point decrease in bleeding intensity according to the 5-point validated bleeding severity scale by each of the defined observation time points (i.e., T4, T7 and T10) will be analyzed using CMH test stratified by type of surgery (i.e., hepatic versus soft tissue surgery).

Also, an ordered categorical analysis of the hemostatic status at each of the assessment time points (i.e., T4, T7 and T10) will be presented. For this, the subjects will be assigned to 1 of 4 categories on the basis of their time to hemostasis (0 to \leq 4 minutes; \geq 4 to \leq 7 minutes; \geq 7 to \leq 10 minutes; \geq 10 minutes). The comparison between treatment groups will be done using an ordinal logistic model assuming proportional odds.

Change from baseline in bleeding intensity according to the 5-point validated bleeding severity scale at the defined observation time points (i.e., T4, T7 and T10) will be summarized. The 5 grades (i.e., 0, 1, 2, 3, and 4) will be considered continuous values in this analysis.

Page 17 of 18

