# 4.3.2 Randomization

Subjects satisfying all pre-operative enrollment criteria will be randomized in 1:1 ratio into the FS Grifols or EVICEL treatment groups. Randomization will be stratified by type of surgery (i.e., parenchymous versus soft tissue surgery) and age groups (i.e., 12-17 years, 2-11 years, 28 days-23 months, and 0-27 days). The investigator site pharmacy will use an Interactive Response Technology (IRT) system to obtain the randomization number and the corresponding assigned treatment (FS Grifols or EVICEL).

At the beginning of the surgical procedure, before any TBS is identified, all materials needed for FS Grifols or EVICEL application will be ready for use. If the subject meets the intra-operative eligibility criteria defined in Section 5.1 and Section 5.2, a randomization number will be recorded in the subject's source documents and electronic Case Report Form (eCRF). If the subject does not meet the intra-operative eligibility criteria, the study drug prepared by the pharmacist will remain unused and discarded according to the respective site standard

procedures. In this case, the IRT system will automatically assign the same treatment to the next subject enrolled in the same stratum.

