2 STUDY DESIGN AND OBJECTIVES

2.1 Study Design

This is a prospective, randomized, active-controlled, single-blind, parallel group clinical trial to evaluate the efficacy and safety of Fibrin Sealant Grifols (FS Grifols) as an adjunct to hemostasis during surgery in pediatric subjects.

Pediatric subjects (<18 years of age) requiring an elective (non-emergent), open (non-laparoscopic), pelvic, abdominal, or thoracic (non-cardiac) surgical procedure, wherein a target bleeding site (TBS) is identified and a topical hemostatic agent is indicated, will be eligible to participate in the clinical trial.

The study treatments will be applied on the cut parenchymous surface of a solid organ (i.e., liver) and in soft tissue (i.e., fat, muscle, or connective tissue).

[figure not shown]
A specific bleeding site will be defined as the TBS when it is determined by the investigator (the surgeon) that control of bleeding by conventional surgical techniques (including suture, ligature, and cautery) is ineffective or impractical and requires an adjunct treatment to achieve hemostasis.

When the TBS is identified, the investigator will record the precise anatomical location of the TBS, rate the intensity of the bleeding at the TBS (Grade 1-4 according to the 5-point validated bleeding severity scale [see Section 3 for the scale]) and record the size of the approximate bleeding surface (small, medium, large). For soft tissue surgery only, the investigator will also record the type of soft tissue (i.e., fat, muscle, or connective tissue). In this clinical trial, only subjects with a TBS with bleeding intensity of Grade 1 (mild) or Grade 2 (moderate) will be enrolled.

Subjects will be randomly allocated in a 1:1 ratio into 1 of 2 treatment groups: FS Grifols or EVICEL. The first 24 subjects to be enrolled in the study will be adolescents (age range 12 to 17 years). The term "enrolled" implies that the subject was actually randomized to and treated with either the FS Grifols or EVICEL. Enrollment will be monitored by surgery type to ensure at least 50% of the surgical procedures are hepatic. Subjects who are randomized and treated with any amount of study drug and withdrawn from the study will not be replaced.

The overall study schema is presented in the figure below:

Page 6 of 18

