For primary efficacy endpoint, subgroup analyses will be provided for surgery type, age group, gender, race, baseline TBS bleeding intensity, and TBS size category.

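### SAP 9.3 summarizes change in bleeding grade without regard to baseline grade, and its ordinal model of time to hemostasis names no factor although randomization is stratified by surgery type

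*SAP*

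**What the plan says.** SAP 9.3 opens with the general rule: "Exploratory efficacy endpoints will be descriptively summarized by treatment group". It then sets out three analyses.

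- The "proportion of subjects achieving at least 1 point decrease in bleeding intensity" at 4, 7 and 10 minutes is compared by a CMH test stratified by surgery type. Baseline grade is not a stratum.
- Time to hemostasis is cut into four ordered categories: "The comparison between treatment groups will be done using an ordinal logistic model assuming proportional odds". No covariate or stratum is named.
- Change from baseline in bleeding grade is summarized at the same time points: "The 5 grades (i.e., 0, 1, 2, 3, and 4) will be considered continuous values in this analysis". No test, interval or model is given.

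Three other places bear on this. SAP 2.1 restricts entry: "only subjects with a TBS with bleeding intensity of Grade 1 (mild) or Grade 2 (moderate) will be enrolled". Protocol 4.3.2 gives the strata: "Randomization will be stratified by type of surgery (i.e., parenchymous versus soft tissue surgery) and age groups". Bleeding grade is not a stratum and cannot be, because the surgeon rates it during the operation, after randomization. SAP 7.1 tabulates baseline grade, and SAP 9.1 lists "baseline TBS bleeding intensity, and TBS size category" among the subgroup factors, but only for the primary endpoint.

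**The concern.** Both bleeding-intensity endpoints are tied to baseline grade by construction. A child who reaches Grade 0 has a change of exactly minus the baseline grade, so the same clinical result scores -1 for a Grade 1 child and -2 for a Grade 2 child. For the 1-point decrease, a Grade 1 child counts only with complete hemostasis, while a Grade 2 child also counts with residual Grade 1 bleeding. An unadjusted comparison of mean change therefore carries any difference between the arms in the share of Grade 2 children, and a reader who compares the two means cannot separate that from a treatment difference.

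The ordinal model raises a separate, smaller matter. Surgery type stratifies the randomization, the primary analysis and the 1-point CMH test, but is not named here. What is at stake is how readable and how efficient the exploratory results are.

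**Working it through.** **Inputs from the documents.** 86 per arm and 80% response in each arm (SAP 4.3). FS Grifols 4-minute hemostasis of 92.8% in the earlier parenchymous-surgery trial and 82.8% in the earlier soft-tissue trial (Protocol 2.2.1.2 and 2.2.1.3).

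**Assumptions not in the documents.** 50% Grade 2 at baseline (range 30% to 70%), response by grade, partial response, and the odds ratios used in the simulation.

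**The plan's own figure.** SAP 9.3 gives no figure. The power statement in SAP 4.3 uses the same 86 and 80%, so it was checked first: SE of the log ratio = sqrt(2 × 0.2 / (0.8 × 86)) = 0.0763; z = 0.2231 / 0.0763 - 1.96 = 0.97; power 83.3%. This agrees with the stated minimum of 80%.

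**Variance of the change score.** Let r be the probability of reaching Grade 0, equal in both grades, with non-responders staying at baseline. Let half the children be Grade 2.

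- Mean change is -r for Grade 1 and -2r for Grade 2, so the between-grade variance is 0.25r².
- Within-grade variance is r(1-r) for Grade 1 and 4r(1-r) for Grade 2, averaging 2.5r(1-r).
- At r = 0.80: between 0.16, within 0.40, total 0.56. Share due to grade = 0.16 / 0.56 = 28.6%. SD falls from 0.748 to 0.632 after adjustment.
- 95% half-width of an arm difference = 1.96 × SD × sqrt(2/86) = 0.299 × SD.

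| Response | Share of variance due to grade | Half-width, unadjusted | Half-width, adjusted | Narrower by |
|---|---|---|---|---|
| 80% (SAP) | 29% | 0.224 | 0.189 | 15.5% |
| 87.8% (equal mix of 92.8% and 82.8%) | 42% | 0.203 | 0.155 | 24% |
| 92.8% | 56% | 0.185 | 0.122 | 34% |
| 95% | 66% | 0.175 | 0.103 | 41% |

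Grade explains half the variance where 0.25r² = 2.5r(1-r), that is r = 10/11, about 91%.

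At roughly 80% overall response, the inputs were varied: Grade 2 share 30% to 70%, Grade 2 response equal to or lower than Grade 1, and 0% to 50% of Grade 2 non-responders falling to Grade 1. The share due to grade runs from 8% to 42%, and the interval would be 4% to 24% narrower.

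**Effect of an imbalance.** A 10-point excess of Grade 2 in one arm moves the difference in mean change by 0.10 × 0.80 = 0.08 grade (0.05 to 0.09 over the same range). The chance SD of the imbalance is sqrt(2 × 0.25 / 86) = 7.6 points, so a typical shift is 0.076 × 0.80 = 0.06 grade, against an unadjusted half-width of 0.22.

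**The 1-point decrease.** With 85%, 90% or 95% of Grade 1 children and 90%, 95% or 98% of Grade 2 children qualifying, the gap between grades is 3 to 5 points. A 10-point imbalance then shifts the rate by 0.3 to 0.5 percentage point.

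**Power of the tested analyses.** Simulation used 4,000 runs per setting, 86 per arm, equal surgery strata, a treatment odds ratio of 2.5 and stratified rank tests. The binary test is a stand-in with the same first cut-off as the ordinal outcome. Moderate covariate effects are odds ratios of 2.0 for surgery and 1.8 for grade; strong effects are 2.7 and 4.

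| Covariate effects | Ordinal: none | Ordinal: surgery | Ordinal: surgery and grade | Binary: surgery | Binary: surgery and grade |
|---|---|---|---|---|---|
| Absent | 78.3% | 78.3% | 77.8% | 77.4% | 76.6% |
| Moderate | 75.8% | 76.8% | 77.4% | 74.4% | 75.1% |
| Strong | 70.9% | 72.8% | 77.0% | 70.5% | 73.6% |

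With no treatment effect, every version rejected in 4.4% to 5.1% of runs, so the omission does not inflate the error rate.

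**The case against.** A reader might infer that the mean change mostly reports which arm had more Grade 2 children. The plan's own 80% response does not support that: grade then explains about 29% of the variance, and it passes half only above about 91%. Such rates are plausible at 7 and 10 minutes or in hepatic surgery, but they are not the planning assumption. Under randomization a chance imbalance is also noise, not bias in expectation.

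A reader might also infer that the plan gives up much precision. For mean change there is no planned test or interval to lose it. For the two comparisons that are tested, the gains are small. The ordinal outcome is time to hemostasis, not bleeding intensity, and is not built on baseline grade. The 1-point CMH test already uses surgery type. The evidence that surgery type is prognostic is mixed: FS Grifols rates differed by 10 points between the two earlier trials, but their Surgicel arms differed by only 2.7 (80.5% and 77.8%).

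Finally, grade is rated by the surgeon after randomization, with the allocated product already prepared, and Protocol 4.3.3 describes blinding of the sponsor only. If ratings differed by arm, stratifying would compare misclassified children within strata and would not repair the bias. The documents do not show that this happens.

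All of this stands, and it limits the point. It does not remove the arithmetic link between baseline grade and the change score. Tabulating grade at baseline lets a reader see an imbalance but not its effect on the change. The SAP's silence on covariates for the ordinal model is also a gap, since every other CMH analysis whose strata are stated uses surgery type.

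**Conclusion.** The point holds as a minor improvement to exploratory analyses. Summarizing change by arm alone leaves in a source of variation that is definitional and already recorded. Under a 50% Grade 2 share with non-responders staying at baseline, a grade-adjusted difference would have an interval about 15% narrower at 80% response and 34% narrower at 92.8%. A 10-point Grade 2 imbalance shifts the unadjusted difference by about 0.08 grade. These figures rest on assumed grade shares and response patterns.

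Naming surgery type in the ordinal model is worth about 1 to 2 points of power and brings it into line with the randomization. Surgery type and grade together add 1.6 to 6.1 points there, of which grade contributes 0.6 to 4.2. Grade adds 0.7 to 3.1 points to the binary CMH test. If neither factor is prognostic, adjustment costs less than 1 point. The primary conclusion is not touched.

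**What to change.** In SAP 9.3, before unblinding:

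- Present change from baseline separately for Grade 1 and Grade 2 children, with an arm difference and interval stratified by baseline grade (or from an ANCOVA on the later grade with baseline grade as covariate).
- Name surgery type as a factor in the proportional-odds model, and say that the odds ratio is conditional on it.
- Optionally, add baseline grade to that model and to the CMH strata for the 1-point decrease.
- Keep the unadjusted summaries alongside, and state that adjustment for a surgeon-rated, post-randomization grade does not correct rating bias.

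The cost is a few lines of SAP text and code, since both variables are already collected. The drawback is thinner strata if grade is added to the CMH test.

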- If the hemostatic effect is incomplete after TStart and before the primary efficacy endpoint at T4, additional amounts of IP may be applied at the TBS up to the maximum allowed volume of 12 mL for subjects greater than or equal to 2 years of age and 6 mL for subjects less than 2 years of age if necessary. It is recommended to remove accumulated blood from the surrounding tissues and the target area to be treated according to normal practice in order to have a dry field prior to application of IP (e.g., by means of suction, sponges or sterile gauzes). These additional applications of IP should be performed via spray or drip application as per the investigator's judgment for soft tissue type and via spray application for parenchymous tissue type. The time of start (TStart2) and end (TEnd2) of IP re-application will be recorded. No additional amounts of IP may be applied beyond the primary efficacy endpoint assessment time point at T4.
- The approximate total amount of IP applied to the TBS and the method(s) of administration (drip or spray) will be documented.
- Subjects in the either treatment group should not receive any alternative hemostatic product or treatment (including application of manual pressure) during the 10-minute observational period, apart from re-application of IP before the primary efficacy endpoint at T4, unless there is Grade 3 or 4 (see Table 7-1) breakthrough bleeding at the TBS that jeopardizes subject safety according to surgeon's judgment, in which case the surgeon may use any other hemostatic measure at his/her discretion (the use of FS Grifols, EVICEL, or other plasma-derived hemostatic agents are not allowed in this case). In this case, the subject will be considered a treatment failure. The alternative treatment applied will be recorded in subject's source documents and eCRF.
- IP can only be applied to the TBS in this study.

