3.1.3 Exploratory Efficacy Variables

- The proportion of subjects achieving at least 1 point decrease in bleeding intensity according to the 5-point validated bleeding severity scale by the defined observation time points of T₄, T₇, and T₁₀
- The mean change from baseline in bleeding intensity according to the 5-point validated bleeding severity scale at the defined observation time points of T₄, T₇, and T₁₀

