4.1 Data Handling

Unless otherwise noted, if an observation is missing at a specific scheduled visit/timepoint, the value at that visit will not be imputed and will be set to missing except for the hemostasis assessment that a missing hemostasis assessment at a time point would be deemed not to have achieved hemostasis at that specific time point only.

Grifols Worldwide Operations, Ltd Page 11 of 18

Unless otherwise noted, baseline will be defined as the last non-missing measurement prior to the start of the study treatment application

This is a single-blind study. Treatment assignment for subjects participating in the study will be blinded from the sponsor, except for personnel from study drug supply groups. Treatment allocation will only be unblinded as necessary within Grifols Global Pharmacovigilance group for subjects that experience a serious and unexpected ADR, as defined in protocol Section 8.3.7, and reported according to the procedure described in protocol Section 8.3.9.1.

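### The two exploratory bleeding-intensity endpoints have no rescue rule, so a grade improved by rescue treatment is credited to the study product

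*SAP*

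**What the plan says.** SAP 3.1.3 lists two exploratory variables on the 5-point scale. The first is "The proportion of subjects achieving at least 1 point decrease in bleeding intensity" by T4, T7 and T10. The second is the mean change in grade at the same three times. Under SAP 9.3, "Exploratory efficacy endpoints will be descriptively summarized by treatment group". The first variable also gets a CMH test stratified by surgery type. For the second, SAP 9.3 plans a summary of "Change from baseline in bleeding intensity according to the 5-point validated bleeding severity scale at the defined observation time points" and specifies the scoring: "The 5 grades (i.e., 0, 1, 2, 3, and 4) will be considered continuous values in this analysis". Protocol 7.1.3 gives the same two variables. None of these places mentions rescue.

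Other endpoints do. The primary variable (SAP 3.1.1) is a failure if there is Grade 3 or 4 bleeding or any alternative hemostatic treatment between the start of application and closure. The T7 and T10 hemostasis variables (SAP 3.1.2.1) also exclude those events and reapplication of study treatment. SAP 3.1.2.2 calls a rescued child a treatment failure, but as an endpoint of its own.

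Protocol 6.1 bars alternative treatment during the 10 minutes unless Grade 3 or 4 breakthrough bleeding jeopardises safety, "in which case the surgeon may use any other hemostatic measure at his/her discretion". The site is assessed at 4, 7 and 10 minutes (Protocol 7.2.1.3.3 and Appendix 1), and no text stops these assessments after rescue.

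On missing data, SAP 4.1 says that "the value at that visit will not be imputed and will be set to missing except for the hemostasis assessment". A missing hemostasis assessment counts as no hemostasis at that time point. No numeric grade is assigned.

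**The concern.** Rescue that follows Protocol 6.1 marks the children in whom the study product did worst. The plan treats rescue as failure for its main endpoints and is silent for the intensity endpoints. Followed literally, SAP 9.3 takes whatever grade is recorded at T7 or T10. If another hemostatic measure has stopped the bleeding, that measure's effect is booked to the study product.

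At stake is how the supporting results read. The responder endpoint will carry a between-arm test, since SAP 4 sets all inference at two-sided 0.05. An arm with more rescue could look level or slightly better on intensity while looking worse on treatment failures, with nothing in the plan to explain the conflict.

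**Working it through.** The plan states no figure for the intensity endpoints. Its only power statement, at least 80% with 86 per arm, concerns the primary ratio. It reproduces on the log-ratio scale: SE = √(2 × 0.2 / (0.8 × 86)) = 0.0763; ln(1/0.8) = 0.2231; Φ(0.2231/0.0763 − 1.96) = 83.3%. It has no bearing on this point.

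**Step 1: what can happen to a rescued child at T7 or T10**

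- *Grade recorded and lower than baseline.* The child is a responder. Graded 0, the change is −1 from baseline Grade 1 or −2 from baseline Grade 2.
- *Grade recorded and still 3 or 4.* The change is a worsening and counts against the arm. An unchanged grade counts as no improvement.
- *Grade missing, mean change.* No number is assigned, so the child drops out.
- *Grade missing, responder endpoint.* The hemostasis exception may apply, because SAP 3.1 uses the same scale to assess hemostasis. No hemostasis means Grade 1 or more. Absent an earlier decrease, a baseline Grade 1 child is then a non-responder, and a baseline Grade 2 child is undetermined.

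**Step 2: effect on one arm's summary**

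Inputs: 86 per arm (SAP 4.3). Assumed: k children break through to Grade 3 after T4, are rescued, and are graded 0 at T10. The swing between the breakthrough grade and the analysed grade is 3 − 0 = 3 points, whatever the baseline.

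- Shift in arm mean = 3k/86. k = 2: 0.07; k = 5: 0.17; k = 8: 0.28.
- Largest shift in T10 responders = k/86. k = 2: 2.3 points; k = 5: 5.8; k = 8: 9.3.

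The responder shift reaches k/86 only if none of the k children had a decrease before rescue. SAP 3.1.3 and 9.3 count a decrease *by* each time point. Read cumulatively, a child already down one grade at T4 is a responder at T10 anyway, so rescue adds nothing.

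**Step 3: effect on the comparison between arms**

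Assumed: non-rescued children are identical in both arms (90% responders, mean change −1.2), mean baseline grade is 1.5, and rescue is r = 15% versus 5%. Responder rate = (1 − r) × 0.90 + r × x. Mean change = (1 − r) × (−1.2) + r × y. Differences are the arm with more rescue minus the other; a negative mean difference favours it.

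| Rescued children | Responders | Difference | Mean change | Difference |
|---|---|---|---|---|
| Credited, Grade 0 (x = 1, y = −1.5) | 91.5% vs 90.5% | +1.0 point | −1.245 vs −1.215 | −0.03 |
| Dropped | 90% vs 90% | 0 | −1.2 vs −1.2 | 0 |
| Failure, Grade 3 (x = 0, y = +1.5) | 76.5% vs 85.5% | −9.0 points | −0.795 vs −1.065 | +0.27 |

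Across rescue rates from 5% versus 2% to 20% versus 5%, failure scoring shows a deficit of 2.7 to 13.5 points and 0.08 to 0.41 grade. Crediting turns this into a gain of 0.3 to 1.5 points. Dropping gives equality. A child still at Grade 3 at the time point already gives the failure row under the plan as written.

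**The case against.** The best defence is that using the grade as observed is a legitimate treatment-policy summary for an exploratory endpoint. Rescue is already visible in the primary endpoint, in the T7/T10 endpoints and in the treatment-failure comparison (SAP 9.2). That stands as a reason for low priority. It does not settle the matter, because the SAP never says that it chose this strategy and its neighbouring endpoints use the opposite one.

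Three stronger readings are tempting, and the documents do not support them.

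- *A rescued child is always either credited or dropped.* Assessment continues after rescue, and a grade that has not improved counts as no improvement or as worsening.
- *Dropping rescued children gives their arm an advantage.* In Step 3 it removes a deficit and leaves the arms equal. Only crediting produces a lead, and a small one.
- *Missing grades have no failure rule at all.* The hemostasis exception can be read to cover part of the responder endpoint. It cannot supply a number for the mean change.

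A practical objection also stands. Breakthrough bleeding between scheduled assessments appears in the SAP 3.1.1 table only as a yes/no item, and no text says that its grade is recorded. A rule based only on the worst recorded grade could miss the breakthrough, so a default is needed.

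**Conclusion.** The point holds as a gap in the two exploratory intensity endpoints. They lack the rescue condition that the plan applies to its primary and T7/T10 hemostasis endpoints. A post-rescue improvement is therefore credited to the study product, and a missing post-rescue grade removes the child from the mean change. Relative to failure scoring, both hide a deficit in the arm with more rescue.

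The size is uncertain because the documents give no rescue rates. The one-arm range of 0.07 to 0.28 grade rests on 2 to 8 assumed children with a 3-grade swing. The responder range of 2.3 to 9.3 percentage points is an upper bound, under the condition in Step 2. Which arm benefits cannot be known in advance. The non-inferiority conclusion does not depend on these endpoints, so this is a desirable correction, not a critical one.

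**What to change.** Add to SAP 9.3:

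- From the first alternative hemostatic treatment, or study treatment after T4, the subject is a non-responder for the one-point-decrease endpoint at that and all later time points. This follows the approach of SAP 3.1.2.1 but is narrower, since it leaves time points before rescue untouched.
- For change from baseline at those time points, whether the grade is observed or missing, use the worst grade up to rescue. A breakthrough that triggered rescue counts as at least Grade 3 if its grade was not recorded.
- Use one wording for the responder endpoint: SAP 2.2.1.3 says *at* the time points, while 3.1.3 and 9.3 say *by*. Under a cumulative reading, state that rescue ends a response gained earlier.
- Keep the as-observed result as a secondary display.

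The cost is SAP wording and a small derivation, to be settled before unblinding. Use of rescue is already collected for the primary endpoint. The documents do not say that its time is recorded, so the SAP should state how rescue is placed relative to T4, T7 and T10 if it is not. The exploratory results would become slightly less favourable where rescue occurs. Nothing in patient management changes.
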